Cover page

Title: Mitigation of radiation pneumonitis and fibrosis

ClinicalTrials.gov Identifier: NCT01754909

Most recent IRB approval Nov 13, 2017

Protocol for “Mitigation of radiation pneumonitis and fibrosis”

Cohen VA 1531-01, CLIN-004-12S

Original from Oct 31, 2012 Registration packet, incorporating amendments through July 2015

Objective

This project will test the effect of enalapril, an angiotensin-converting-enzyme inhibitor, to mitigate radiation pneumonitis and fibrosis in veterans undergoing radiation therapy for lung cancer and other cancers in the chest. It is based on the hypothesis that human normal tissue radiation injury can be safely and effectively mitigated, and on our extensive studies of radiomitigation in experimental animals. Lung cancer is more common in veterans than in the general population; this project is highly relevant to the medical care of veterans.

Research design and methodology

Enalapril or placebo will commence after the start of irradiation in veterans undergoing radiation therapy for lung cancer and other cancers in the chest, and their effects on radiation pneumonitis and fibrosis will be compared as the primary outcome measure. Enalapril will be used rather than captopril, because enalapril is given in single daily doses. This is a prospective, double-blinded, randomized, placebo-controlled trial, in a secondary-tertiary care setting. Subjects will join this trial voluntarily, based on their planned radiotherapy for lung cancer, and it is planned to enroll 200 subjects over the five years of this study. The intervention of this study is the use of enalapril or placebo, which will be maintained for the lifetime of the study subject.

2. To test the mechanism of mitigation of radiation lung injury by enalapril.
 - a. Angiotensinogen, plasma renin activity, and angiotensin II will be measured as renin-angiotensin system markers in all subjects.
 - b. The effect of enalapril on each marker will be assessed, as compared to placebo.
3. To confirm that enalapril in this use does not adversely affect cancer treatment outcomes.
 - a. Cancer recurrence and death from cancer will be compared for the enalapril and placebo groups.

These studies will be done in men and women undergoing radiation therapy for lung cancer and other cancers in the chest. Enalapril, or identical-appearing placebo, will be started within a day

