to up to 30 days of the beginning of the radiation treatments. The effect of the enalapril or placebo will be tested by their effect to reduce grade 2 or greater clinical radiation pneumonitis, by their effect on the renin-angiotensin system markers angiotensinogen, plasma renin activity, angiotensin II, and their effect to reduce radiographic evidence of pneumonitis and fibrosis.

NARRATIVE SUMMARY - HUMANS

1. **PURPOSE.** Provide the purpose or objectives of the study. Do not indicate "N/A" for this category.

To test the benefit of enalapril, an angiotensin-converting-enzyme-inhibitor, to mitigate radiation pneumonitis and fibrosis in humans.

2. **SCIENTIFIC RATIONALE.** Provide the reasons for doing the study. Do not indicate "N/A" for this category.

This project will test the effect of enalapril, an angiotensin-converting-enzyme inhibitor, to mitigate radiation pneumonitis and fibrosis in veterans undergoing radiation therapy for lung cancer and other cancers in the chest. It is based on the hypothesis that human normal tissue radiation injury can be safely and effectively mitigated, and on our extensive studies of radiomitigation in experimental animals. Lung cancer is more common in veterans than in the general population; this project is highly relevant to the medical care of veterans.

3. **BACKGROUND.** Provide information from previous studies leading up to this study, either from your laboratory or from those of others. If this is a treatment study involving investigational drugs, devices, or therapies, standard treatment must be clearly identified. Do not indicate "N/A" for this category.

Lung cancer is an important health problem for veterans. It is more common in them than in the general population, and lung cancer survival is less in veterans. Radiation therapy for lung cancer is used in over half of the cases, and it can be followed by radiation pneumonitis and fibrosis. These add significant morbidity and mortality, and they limit the doses of curative irradiation. Standard treatments for radiation pneumonitis and fibrosis are very limited. Mitigation is a new approach, being the use of an agent after initial irradiation but before the expression of radiation injury.

Our studies in rats show significant mitigation of radiation pneumonitis and fibrosis by angiotensin converting enzyme (ACE) inhibitors.

Our recent clinical trial shows the mitigation of radiation nephropathy by the ACE inhibitor captopril.

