Cancer-related survival and cancer recurrence will be compared for the enalapril and the placebo groups using Kaplan-Meier statistics. [We have calculated our ability to detect significant changes in cancer recurrence rates and in cancer survival, both for improvements in cancer-related outcomes and for adverse trends. We will be able to detect significant increases in recurrence rates or mortality. Our cohort of 162 subjects showed no difference in patient survival for those on ACE inhibitor compared to those not on ACE inhibitor. We do not

expect adverse changes in recurrence rates or patient survival. A mitigation benefit by enalapril could lead to an increase in patient survival, but less than a three month increase is not likely to be detected]

Recurrence rate change	Percent chance of detection
40 to 20 %	80%
40 to 60 %	81%

Cancer median survival change, months	Percent chance of detection
18 to 21	11%
18 to 12	60%

[There are potential pitfalls in the recurrence and survival analyses. These include the effects of interim sampling for the safety analyses, and adjustments for patient and disease characteristics as well as missing data.] The interim masked safety analyses will use the O'Brien correction to take into account the multiple analyses. In our analysis of survival, we will compare the recurrence-free survival rates between the treatment arms of the study in two ways. First we will examine the rates of death or recurrence using a Cox model. In this model we will adjust for patient/disease characteristics such as site of treatment, gender, age, stage of disease at randomization, and radiation dosage. We will also compare the disease free survival probabilities at two years using techniques that we have published (52). This method allows us to deal with the partial information available in patients who do not have a potential follow-up time of two years. This approach, which is a censored data version of logistic regression, will allow us to adjust the comparisons for patient, disease, and treatment factors. We picked two years here since the empirical evidence is that the disease-free survival curves tend to flatten out at around 20 months.

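### Aim 3's only covariate-adjusted models use death or recurrence instead of the cancer endpoints the aim names, so prevented toxic deaths would dilute a cancer harm in them

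*SAP*

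**What the plan says.** The protocol (Research design and methodology, aim 3) sets the purpose: "To confirm that enalapril in this use does not adversely affect cancer treatment outcomes". It names the endpoints: "Cancer recurrence and death from cancer will be compared for the enalapril and placebo groups".

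The SAP section *Survival analysis for aim 3* starts from the same two endpoints: "Cancer-related survival and cancer recurrence will be compared for the enalapril and the placebo groups using Kaplan-Meier statistics". Its power table is also built on recurrence rate and median cancer survival.

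Later in that section the event changes: "we will compare the recurrence-free survival rates between the treatment arms of the study in two ways". The first way is "First we will examine the rates of death or recurrence using a Cox model", adjusted for site, gender, age, stage and radiation dose. The second is "We will also compare the disease free survival probabilities at two years using techniques that we have published", a censored-data form of logistic regression that also allows adjustment. No adjusted model is named for recurrence alone or for cancer death, and the cause of death is not specified in the Cox sentence.

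Two other statements bear on the direction of any effect. Of pneumonitis and fibrosis, the protocol (section 3, Background) says: "These add significant morbidity and mortality, and they limit the doses of curative irradiation". The SAP says: "A mitigation benefit by enalapril could lead to an increase in patient survival", and adds that a gain of less than three months would probably go undetected.

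**The concern.** Aim 3 is a harm check. Its question is whether cancer control is worse on enalapril. A composite of recurrence and any death answers a different question, because it mixes the cancer effect with the effect on non-cancer deaths.

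The documents themselves allow these two effects to run in opposite directions. If enalapril protects the lung, fewer patients die of lung toxicity and the composite moves in the drug's favour. If enalapril also raises recurrence, the composite moves against it. The adjusted hazard ratio is then pulled towards 1, which for a harm check is the unsafe direction.

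The SAP does not say which analysis decides aim 3. If the unadjusted cancer curves suggested harm and the adjusted composite did not, the plan gives no rule for the conclusion.

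**Working it through.** **1. The plan's own figure.** The SAP gives an 81% chance of detecting recurrence rising from 40% to 60%. A two-proportion test with 100 per arm, two-sided 0.05, pooled variance and no continuity correction gives 81.2%. The figure reproduces, and it refers to recurrence alone.

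**2. Inputs for the Cox comparison.**
- From the documents: 200 subjects in total; enrollment over five years; 40% to 60% recurrence.
- Assumed: 100 per arm; two-sided 0.05; the recurrence figures are two-year rates; constant hazards; uniform accrual analysed at year 5, so censoring is uniform on 0-60 months.
- Not in the documents: the rate of toxic death without recurrence. A range is shown. The cut in these deaths is set at 50% or 80%. The 80% borrows the SAP's mitigation figure, which is for pneumonitis incidence, not deaths.

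**3. Formulas.**
- Cancer hazard on placebo: λc = −ln(0.6)/24 = 0.02128 per month.
- Cancer hazard ratio: ln(0.4)/ln(0.6) = 1.79.
- With s the share of placebo events that are toxic deaths and HRn their hazard ratio: composite HR = (1 − s) × 1.79 + s × HRn.
- Two-year placebo toxic-death risk = s × (1 − exp(−24λ)), where λ = λc/(1 − s).
- Proportion with an event in an arm with total hazard λ = 1 − (1 − exp(−60λ))/(60λ).
- Power = Φ(√(d/4) × ln HR − 1.96), with d the total events.

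**4. Worked case, s = 10%, deaths halved.** λ = 0.02128/0.9 = 0.02365, so the two-year toxic-death risk is 0.1 × (1 − exp(−0.5676)) = 4.3%. Composite HR = 0.9 × 1.794 + 0.1 × 0.5 = 1.66. Events are 46.6 + 61.6 = 108.2. Power = Φ(5.20 × 0.509 − 1.96) = Φ(0.69) = 75%. For the cancer-specific event d = 101.7, and power = Φ(5.04 × 0.584 − 1.96) = Φ(0.99) = 84%.

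**5. Results.**

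| Two-year placebo toxic-death risk | Share s | Cut in toxic deaths | Composite HR | Composite power | Cancer-specific power |
|---|---|---|---|---|---|
| 2% | 4.8% | 50% | 1.73 | 81% | 84% |
| 2% | 4.8% | 80% | 1.72 | 79% | 84% |
| 3% | 7.1% | 50% | 1.70 | 79% | 84% |
| 3% | 7.1% | 80% | 1.68 | 76% | 84% |
| 4.3% | 10% | 50% | 1.66 | 75% | 84% |
| 4.3% | 10% | 80% | 1.63 | 72% | 84% |

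Part of this loss needs no drug effect on toxic deaths. With HRn = 1 and s = 10%, composite power is already 80%.

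**6. A second method, closer to the two-year model.** Adding toxic deaths q to 40% against 60% recurrence and using two proportions gives 77% (deaths halved) or 74% (cut by 80%) at q = 2%, and 70% or 62% at q = 5%. The direction is the same and the loss somewhat larger.

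**7. Limits of plausibility.** The SAP's clinical pneumonitis rate is 11%, non-fatal cases included. A toxic-death risk of 4.3% would already mean 4.3/11 = 39% of cases are fatal. Shares of 20% and 30% imply risks of 9.4% and 15.5%. The first needs 9.4/11, about 86%, of cases to be fatal, and the second needs more deaths than cases. Composite power in those rows (62% or 54%, and 46% or 31%) is therefore not a fair summary. Fibrosis deaths could add to the total, but no rate is given.

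**The case against.** The strongest reply is that the aim's endpoints are already tested. The Kaplan-Meier comparison uses recurrence and cancer-related survival, the trial is randomized, and an unbiased comparison of arms does not need covariate adjustment. Nothing in the SAP makes the composite decisive. This stands: a reader might infer that aim 3 has lost its cancer endpoints, and the text does not support that. Only the adjusted models are affected.

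A reader might also infer that the composite could cancel or hide a cancer harm. The figures do not show this. Even in the extreme row (30% share, 80% cut) the composite hazard ratio is 0.7 × 1.79 + 0.3 × 0.2 = 1.32, so the effect is dilution.

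Nor is the stated 81% wrong. It stands in a recurrence table, reproduces there, and is not claimed for the Cox composite.

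The trial's hypothesis is that pneumonitis and fibrosis occur less often, not that toxic deaths fall. An effect on such deaths is something the documents allow for, without giving a rate.

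Finally, recurrence-free survival is a conventional endpoint that avoids attributing cause of death, which is difficult when a patient has both lung injury and tumour. That is a good reason to keep it as a supportive analysis. It is a weaker reason to make it the only adjusted one, because aim 3a already requires deaths from cancer to be identified. If death in the Cox sentence was meant as cancer death, most of the point reduces to a clarification.

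**Conclusion.** The point holds for the adjusted models only. Aim 3 and the Kaplan-Meier analysis are cancer-specific, while the adjusted Cox and two-year models, read plainly, are not. A drug effect on toxic deaths, which the documents foresee, would weaken a cancer-harm signal in those models. Under the constant-hazard assumptions above, and with a placebo toxic-death risk of about 2-4% at two years, power against the SAP's own harm scenario falls from about 84% to about 72-81%. Larger losses need toxic-death rates that are hard to square with an 11% pneumonitis rate. The size rests on a rate the documents do not give, and on reading death as any cause. It is an inexpensive improvement to a harm check that is otherwise present in the plan.

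**What to change.** In the SAP section *Survival analysis for aim 3*:

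- Fit the same adjusted Cox and two-year models to time to recurrence and to time to cancer death, with non-cancer death as a competing event (cause-specific hazards in the Cox model).
- Keep the composite of death or recurrence as a supportive analysis.
- State that the conclusion on cancer harm is read from the cancer-specific analyses.
- Say whether death in the Cox sentence means any cause.

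The cost is a few sentences and further runs of models already planned. The cancer-specific models have somewhat fewer events (about 102 against 108 in the worked case), yet higher power against this harm in every row of the table. They depend on classifying cause of death, which aim 3a already requires; doing this blind to treatment arm would protect it.

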Our retrospective clinical studies show that concurrent use of ACE inhibitors reduces the occurrence of radiation pneumonitis [and fibrosis], without lowering cancer-related survival. The safe mitigation of radiation injury has been identified as a priority by the National

Cancer Institute. We will address this critical problem. We hypothesize that the occurrence of radiation pneumonitis, fibrosis, or both in patients receiving radiation for lung cancer will be decreased by the ACE inhibitor enalapril, started after irradiation.

4. STUDY DESIGN. Provide a brief description of the design of the study (multicenter, double-blind, randomized, etc.) in narrative form. Do not provide details of specific procedures in this section (see Item 9 below). Include, as needed, a discussion of the appropriateness of research methods. Describe the statistical design and required sample size. Do not indicate "N/A" for this category.

This is a prospective, double-blinded, randomized, placebo-controlled trial, in a secondary-tertiary care setting. The ZVAMC and referring VAs in VISN 12 are the main centers; the Baltimore VAMC will be added. Subjects will join this trial voluntarily, based on their planned radiotherapy for lung cancer. We will enroll 200 subjects over the five years of this study. Statistical power analysis suggests the need for 200 subjects for the clinical endpoint, and ~ 100 subjects for the radiographic endpoint.

5. SUBJECT SELECTION AND EXCLUSION CRITERIA. Provide the specific criteria for including and excluding subjects in the study. Do not indicate "N/A" for this category.

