The study drug, enalapril or placebo, will be in addition to usual clinical care of subjects undergoing radiation therapy for lung cancer. Enalapril, or placebo, will be given orally, started within a day to up to 30 days of the beginning of the radiation treatments. They will be enrolled at the start of radiation therapy (RT), stratified for cancer stage, then randomized to enalapril or identical-appearing placebo. Randomization will be done by the Department of Biostatistics, Medical College of Wisconsin, using random number tables; the center pharmacies will be notified of the assignment to enalapril or placebo. There will be no stratification by age, gender, lung cancer histology, or use of chemotherapy since these do not have a consistent relation with the occurrence of RP. There is no stratification by center. Study drug is obtained from Expert Pharmacy Inc, with identical appearing enalapril and placebo tablets. It is held in the VA research pharmacy at Milwaukee, in a restricted access area under the aegis of the research pharmacist. It will be sent to patients at the Baltimore site upon their enrollment. The study drug dose will be

2.5 mg to start, and will be increased in increments of 2.5 mg to 10 mg per day, as tolerated. Clinical follow up of study subjects will be identical to that of subjects undergoing radiation therapy for lung cancer but who are not participating in this study, with the addition of four blood samples. One blood sample one week after starting the study will be to check for adverse effects of the study drug. Three more blood samples will be obtained for renin-angiotensin system (RAS) assays, done on three blood samples from each subject, at the start of the study, at 3 weeks after the start, and at the end of radiation therapy. Each of these four research-related blood samples will be approximately one teaspoon of blood obtained by venipuncture. Compliance is assessed by monitoring the requests for study drug refills. It will be verified at the end of the study by the elevation in plasma renin in subjects on enalapril compared to those on placebo. Study subjects will be monitored for adverse effects of study drug. The development, or not, of radiation pneumonitis and fibrosis will be assessed in the study subjects, as part of ongoing regular care, as are the periodic radiographic imaging and lung function testing. Quality of life will also be assessed.

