Cover page

Mitigation of radiation pneumonitis and fibrosis

ClinicalTrials.gov Identifier: NCT01754909

Most recent IRB approval Nov 13, 2017

Statistical methods plan

Power analysis for aim 1

For the RP endpoint, at an 11% rate of clinical RP, and an 80% mitigation effect, 97 subjects are needed per arm for type 1 error of 0.05 and a power of 0.80. The 11% and 80% figures are based on our retrospective studies. Only 49 are needed per arm for a baseline clinical RP rate of 20%. We plan for 200 subjects because there is variability in the rate of RP, and because we cannot be certain about the magnitude of efficacy of enalapril.

control	%difference	treatment	n/arm	total n
11%	50%	6%	306	612
11%	60%	4%	199	398
11%	70%	3%	136	272
11%	80%	2%	97	194
11%	90%	1%	70	140
20%	50%	10%	155	310
20%	60%	8%	101	202
20%	70%	6%	70	140
20%	80%	4%	49	98
20%	90%	2%	36	72

For a 50% radiographic rate of RP, and a halving of this by enalapril, 45 subjects are needed per arm.

50%	50%	25%	45	90
-----	-----	-----	----	----

50%	60%	20%	30	60
50%	70%	15%	21	42
50%	80%	10%	15	30
50%	90%	5%	11	22

For the radiographic fibrosis endpoint, at a 90% fibrosis rate, 29 subjects per arm would identify a 30% reduction in radiographic fibrosis at 6 or 12 months.

Endpoint and RAS analyses

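### The 81% power for a rise in recurrence matches 100 fully observed subjects per arm, which the plan does not assure, and that basis does not reproduce the 80% in the row above it.

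*SAP*

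**What the plan says.** The SAP section on survival analysis for aim 3 asserts: "We will be able to detect significant increases in recurrence rates or mortality". For recurrence, the support is a two-row table whose result column is headed "Percent chance of detection": 40 to 20% has 80%, and 40 to 60% has 81%. Neither row states the number per arm, the alpha, the time by which the rates are reached, or any allowance for incomplete follow-up.

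The same section plans Kaplan-Meier comparisons of cancer-related survival and recurrence, then a Cox model for death or recurrence, then a comparison of disease-free survival at two years by a censored-data form of logistic regression. Of that last method it says: "This method allows us to deal with the partial information available in patients who do not have a potential follow-up time of two years". It also expects disease-free survival curves to flatten at about 20 months.

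On timing, the protocol's section on research design says that "it is planned to enroll 200 subjects over the five years of this study", and its Study Design item repeats this: "We will enroll 200 subjects over the five years of this study". The text available states no minimum follow-up after the last enrolment and no data cut-off.

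**The concern.** If enrolment takes up the whole study period, late entrants contribute little follow-up. A censored-data method uses what they do contribute without bias, but it cannot restore outcomes that were never observed. A power figure for complete observation would then be too favourable.

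Aim 3 is meant to confirm that enalapril does not worsen cancer outcomes, so a null result will be judged by the chance that harm would have been seen. The 40 to 60% row is the only support for the recurrence part of the SAP's claim. At 81% power, a 20-point rise is missed 19% of the time; at 71%, it is missed 29% of the time. The reader cannot tell which applies, and the companion row points to a different basis.

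**Working it through.** **Inputs.** From the documents: 200 subjects over 60 months; recurrence 40 v 60% and 40 v 20%; alpha 0.05, stated only for aim 1 ("97 subjects are needed per arm for type 1 error of 0.05 and a power of 0.80"); flattening at about 20 months. Assumed: two-sided 0.05 for aim 3; 1:1 allocation, 100 per arm (the ratio is not stated, but the aim 1 table uses equal arms); uniform accrual; no loss other than administrative censoring.

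**1. Reproduce the 81%.** Pooled two-proportion test, all outcomes known:

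power = Φ{[|p1−p2|√n − 1.96√(2p̄(1−p̄))] / √[p1(1−p1)+p2(1−p2)]}

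n = 100, 0.40 v 0.60: (2.000 − 1.386)/0.693 = 0.886, so power is 81.2%. The printed figure reproduces.

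**2. Same basis, companion row.** n = 100, 0.40 v 0.20: (2.000 − 1.270)/0.632 = 1.154, so power is 87.6%. The SAP prints 80%. Continuity correction (84.0%) and Fisher's exact test (84.4%) do not reach 80% either.

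**3. What would give about 80% for 40 to 20%?**

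| Basis | 40 to 20% | 40 to 60% |
|---|---|---|
| Printed | 80% | 81% |
| 100 per arm, fully observed | 87.6% | 81.2% |
| 82 per arm, fully observed | 80.4% | 73.0% |
| 100 per arm, Kaplan-Meier at 24 months, analysis at month 60 | 79.3-81.3% | 71.1-73.5% |

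No single sample size and formula tried gives both printed values.

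**4. Effect of incomplete follow-up on 40 v 60%.** With analysis at month 60, potential follow-up is uniform on 0 to 60 months, so 24/60 = 40% of subjects have less than two years. The proportion still under observation at month t is G(t) = 1 − t/60. The Greenwood variance per subject is

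V = S(24)² ∫ λ(t)/[S(t)G(t)] dt,

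and power = Φ{0.2/√[(V1+V2)/100] − 1.96}.

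- Constant hazard to 24 months: V1 = 0.3132 and V2 = 0.3184, against 0.24 each with full observation. 0.2/0.0795 − 1.96 = 0.557, so power is 71.1% (simulation, 20,000 runs: 70.6%).
- Rates reached by 20 months, no events after: V1 = 0.2970 and V2 = 0.3009, so power is 73.5% (simulation: 73.0%).
- The same formula with full observation gives 82.3%, the like-for-like comparator.

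**5. Later analysis.** With 60 months of accrual and 12 months more, 12/60 = 20% are short of two years and power is 79.6-80.9%. With 24 months more, none are short and power is 82.3%. If the 12 months are instead taken out of the 60, power is 78.8-80.5%.

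**6. Log-rank or Cox, analysis at month 60.** HR = ln(0.4)/ln(0.6) = 1.794 and power = Φ{ln(HR)√D/2 − 1.96}, with D the number of events.

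- Events stop at 24 months: D = 82.5, power 75.6%.
- Events stop at 20 months: D = 85.4, power 77.0%.
- Hazard constant throughout: D = 104.3, power 84.7%.
- Full observation, for comparison: D = 100, power 83.2%.

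**The case against.** A reader might infer that the SAP's two-year comparison has 71% power where 81% is claimed. The documents do not support that, for four reasons.

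- **Time point and endpoint.** The 81% is tied to no time point. The two-year comparison is of disease-free survival, where death counts as an event. The SAP's own table starts from a median cancer survival of 18 months; if that is the control value, more than half of control subjects have had an event by two years, so a 40% control rate cannot apply there.
- **Analysis date.** Analysis at month 60 with no follow-up after the last enrolment is an assumption, and the least favourable one. Twelve further months recover nearly all of the loss.
- **Order of analyses.** The Cox model comes first and uses all follow-up. Its 76-85% spans the printed figure, although the 85% needs a constant hazard past two years, contrary to the flattening that the SAP expects.
- **Censoring may not have been ignored.** A reader might also infer that the table makes no allowance for censoring. The survival rows suggest otherwise: with all 200 deaths observed, 18 to 12 months has 81.8% power and 18 to 21 months 19.2%, while the SAP prints 60% and 11%. Uniform five-year accrual with analysis at month 60 gives 64.8% and 13.0%. A censored log-rank calculation with 90 per arm and constant hazards also gives 80.8% for 40 to 60%. It gives 89.5% for 40 to 20%, however, so it does not explain the table either.

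All four stand, and together they rule out an unconditional 71%. They do not remove the conflict between the two recurrence rows, or the absence of any stated basis for a figure on which aim 3 relies.

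**Conclusion.** The concern holds in a limited form. The 81% agrees with full observation of 100 per arm, but agreement does not prove that this was its basis, and the plan does not assure such follow-up.

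For recurrence of 40 v 60%, with 100 per arm, uniform 60-month accrual and analysis at month 60, power is about 71-73% for a two-year Kaplan-Meier comparison. Varying event timing and test scale widens this to about 67-78%. Log-rank or Cox has about 76-77% if events stop by 20 to 24 months, and 85% under a constant hazard. With 12 months of follow-up after the last enrolment the two-year figure is about 80%, and with 24 months about 82%. The shortfall against the printed figure therefore runs from nothing to about 10 points, depending on an analysis date that the text available does not give. If the full protocol states a follow-up period, that value settles the matter.

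The inconsistency between the rows needs no accrual assumption. A basis that gives 81% for 40 to 60% gives 87.6% for 40 to 20%, and a basis that gives about 80% for 40 to 20% gives only about 71-73% for 40 to 60%.

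**What to change.** In the SAP section on survival analysis for aim 3, recompute both recurrence rows on one stated basis: number per arm, alpha and sidedness, the time by which the rates apply, accrual pattern, analysis date, handling of censoring (including death without recurrence), and the test actually planned. Replace the printed 80% and 81% with the results. If power is also wanted for the two-year disease-free survival comparison, calculate it from event rates for death or recurrence, not from 40% and 60%. Reword the claim that increases in recurrence or mortality will be detected so that it matches the recomputed figures.

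The cost is one recalculation and a few sentences. The stated power for harm may become up to about 10 points less favourable. No extra subjects or procedures are needed.
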